4.2.4 Randomization

Randomization will be performed in a 1:1 fashion by sealed opaque envelopes and treatment assigned by random number generation done in blocks. Patients will be randomized immediately following insertion of the endovascular cooling catheter. Because patients with ventricular tachycardia (VT) or ventricular fibrillation (VF) have better survival than other rhythms¹⁰ patients will be stratified based on their initial rhythm. Patients with an initial rhythm of either VT or VF will be randomized from a different series of envelopes than patients with an initial rhythm of asystole or pulseless electrical activity (PEA). The two different series of randomization

envelopes will be identifiable and differentiable by coding (ie. VT/VF randomization codes will begin by the number 1, while randomization codes for asystole/PEA will begin by the number 2). This will ensure balancing in the groups in this important prognostic factor.

4.2.5 Blinding

The treating physician and patient will be blinded to group allocation. The only member of the health care team who is not blinded will be the treating nurse as temperature adjustments on the cooling catheter will be performed by the nurse as per protocol. Nurses will chart temperature in a separate log, as per usual. This log, however, will be kept in the patient's room and will not be a part of the medical records that the physician has routine access to. Randomization documents will be collected by nurses and or the study coordinator to ensure blinding.

Outcomes will be adjudicated by an independent, blinded committee. Cardiologists performing the follow-up assessments will be blinded. Rehabilitation physicians performing the cognitive assessments will be blinded to group allocation.

4.2.6 Participation Consent

This study, complies with the Tri-Council Policy Statement 2 (TCPS 2) guidelines from Chapter 3, Sections 3.8, 3.9 and 3.10. for obtaining proper consent from the participants and or from their authorized third party.

4.3 Interventions

Eligible patients will be randomized to mild TH (goal cooling temperature of 34°C) or moderate TH (goal cooling temperature of 31°C). The rate of cooling to the signed temperature after randomization will be on the basis of as fast as technically feasible by the device. Cooling will be performed via an endovascular cooling device (ZOLL Medical Corporation, Chelmsford, MA) inserted via the femoral vein into the inferior vena cava either in the cardiac catheterization laboratory or in the coronary care unit. Our current practice is to target 33°C with the identical protocol. Paramedics and transferring facilities will be encouraged to initiate hypothermia with ice packs as soon as possible (prior to arrival at the University of Ottawa Heart Institute). This is done by placing ice packs to the neck, groin and axilla.

Upon presentation to the University of Ottawa Heart Institute, patients may be taken to the cardiac catheterization laboratory at the discretion of the treating team for coronary angiography and/or insertion of a mechanical support device (intra-aortic balloon pump).

All patients will be sedated, intubated and ventilated. The University of Ottawa Heart Institute standard cooling protocol will be used to implement sedation, analgesia and neuromuscular blockade. Paralytic agents will be used during the cooling process to inhibit shivering. All of these medications and monitoring are currently the standard of care. The temperature will be recorded via the ZOLL catheter. Patients will have nasopharyngeal and bladder temperature probes inserted to correlate with temperatures monitored intravascularly.

Patients who present to the Ottawa Heart Institute with body temperatures $<34^{\circ}\text{C}$ can still be randomized to one of the groups. The temperature will be adjusted with the endovascular cooling device according to the randomly assigned temperature. Note that the device is capable at cooling or warming to the set target temperature.

Patients will be maintained at their assigned cooling temperature for a duration of 24 hours after reaching target temperature. Following the mandated 24-hour cooling period, patients will be actively re-warmed at a rate of $0.25^{\circ}\text{C}/\text{hour}$ until normothermia (36.5°C) is reached. Normothermia will be maintained for 48 hours from the time of initiation of re-warming with active management of the temperature via the ZOLL catheter. This is the current standard of practice at the University of Ottawa Heart Institute.

If, in the opinion of the blinded treating physician, cooling is contributing to intractable arrhythmia, or hypotension refractory to vasopressor use, then the treating physician may choose to abandon cooling. In this situation the temperature of the patient will be increased by 3°C (i.e. from 31°C to 34°C or from 34°C to 37°C). The treating physician will remain blinded to group allocation. If, despite the increased temperature, it is believed that cooling is still contributing to significant adverse events, the physician can request to raise the temperature again (34 to 37°C and if at 37°C then no change will be made). Blinding will be maintained.

The patient's dedicated nurse will perform all temperature changes on the ZOLL[®] machine. The nurse is the only member of the health care team that is unblinded to group allocation – for logistical reasons, blinding of the nurse is not feasible.

Aside from the difference in cooling temperatures, management in the coronary care unit and subsequently on the cardiology wards will be standard of care. Again, both the treating physicians and the patient will be blinded to treatment allocation to ensure assessment of outcomes remains unbiased.

4.4 Laboratory Assessments

Total creatinine kinase (CK) and troponins will be assessed on admission and q8h x 24 hrs. A complete blood count (CBC) will be obtained immediately upon admission and repeated daily x3, and thereafter as indicated. A CBC will be repeated anytime that there is evidence of overt bleeding. Initial blood work will include electrolytes and serum creatinine and repeated daily x3. An ECG will be done immediately after a PCI, and daily x3. An ejection fraction will be obtained within 1 week of admission and at 90 days. This can be obtained by echocardiography, radionuclear imaging (LV Gated scan) or by magnetic resonance imaging (MRI). The imaging at 90 days should be the same imaging modality as was used initially.

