3.6 Statistical Analyses

3.6.1 Sample size

A total of 340 patients will be required to detect an absolute 15% risk reduction (30% relative risk reduction) in the primary outcome based on an anticipated event rate of 50% in the mild hypothermia group and of 35% in the moderate hypothermia group using a chi-square test for comparing proportions with alpha set of 0.05 and a power of 80%.

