5.2 Secondary Outcomes

- 1) Death during the initial hospitalization, at 30 days and at 6 months
- 2) Stroke during the initial hospitalization, and at 6 months
- 3) TIMI minor/major bleeding during first hospitalization (+7 days)
- 4) Length of stay in the unit
- 5) Length of stay in the hospital
- 6) Cardiogenic shock during the initial hospitalization
- 7) Repeat circulatory arrest requiring cardiopulmonary resuscitation (CPR)
- 8) Arrhythmia requiring anti-arrhythmic medication (aside from beta blocker)
- 9) Presence of seizures
- 10) Renal failure requiring renal replacement therapy
- 11) Ventilator associated pneumonia
- 12) LV function assessed by echo done on day 3 and at 90 days
- 13) CK release within first 48 hrs.
- 14) Frequency of Stent thrombosis
- 15) Discharged home.

All clinical events will be adjudicated by a committee utilizing the abovementioned definitions in a blinded manner. As noted, rehabilitation physicians performing the neurologic assessments will be blinded to group allocation.

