7. STATISTICAL AND ANALYTICAL METHODS

All analyses on the primary outcome and its components will be performed on an intention-to-treat. The primary outcome will be compared between treatment arms using a significance level of 5% and a power of 80%. Secondary outcomes will be examined using parametric or non-parametric statistics as appropriate for the scale of measurement of the dependent variables. Analyses will be conducted using SAS.

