8. SAMPLE SIZE

8.1 Sample Size

Outcome measures for all randomized patients will be analyzed in an intention-to-treat analysis. The primary outcome of our study will be a composite of 1) death or 2) poor neurologic outcome, at 6 months. Based on our review of the literature and our own cardiac arrest database we estimate an event rate of 50% in the mild TH group. To detect a 30% relative risk reduction with 80% power and a type I error of 5% will require a sample size of 340 patients (170 per temperature group).

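### The analysis of CK release (secondary outcome 13) is not specified beyond a test chosen by measurement scale, and the plan does not say that admission CK or rhythm stratum will be used

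*Combined protocol and SAP*

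**What the plan says.** - **Sampling (4.4).** "Total creatinine kinase (CK) and troponins will be assessed on admission and q8h x 24 hrs". If the eight-hourly draws fall at 8, 16 and 24 h, each patient has one admission value and three later ones.
- **Outcome (5.2, item 13).** "CK release within first 48 hrs". Neither 5.2 nor section 6 says whether this means a peak, an area under the curve or a rise from admission.
- **Analysis (7).** "Secondary outcomes will be examined using parametric or non-parametric statistics as appropriate for the scale of measurement of the dependent variables". No model, transformation or covariate is named for any secondary outcome. Section 7.3 compares the groups descriptively and does not mention admission enzymes.
- **Timing of allocation (4.2.4).** "Patients will be randomized immediately following insertion of the endovascular cooling catheter". Section 4.3 places the insertion in the catheterization laboratory or the coronary care unit.
- **Stratification (4.2.4).** VT/VF and asystole/PEA patients are drawn from separate envelope series because rhythm is prognostic. Section 7 does not say that the analysis will use this stratum.

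**The concern.** CK already in the blood on arrival reflects the arrest and resuscitation, and the assigned temperature cannot have changed it. If later CK is compared between arms without regard to that value, differences between patients on arrival stay in the error term. A chance imbalance in admission CK then moves the estimate. The same holds for rhythm to the extent that it predicts CK.

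The silence also leaves choices open. Peak, area under the curve, change from admission, raw or log scale, adjusted or not: all fit the present wording, so the choice could be made after the data are seen. At stake are the precision and prespecification of one of 15 secondary outcomes.

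**Working it through.** **1. The plan's own figure.** The documents give no sample-size figure for CK, so the only check is on the number per arm. Section 3.6.1 uses an "anticipated event rate of 50% in the mild hypothermia group and of 35% in the moderate hypothermia group", alpha 0.05 and 80% power. For a two-sided test with pooled null variance and no continuity correction:

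n per arm = [1.960 × √(2 × 0.425 × 0.575) + 0.8416 × √(0.50 × 0.50 + 0.35 × 0.65)]² / 0.15² = (1.370 + 0.582)² / 0.0225 ≈ 169.3, rounded up to 170.

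The total is 340, as in 8.1, and power at 170 per arm is 80.2%. The 170 is carried forward below; nothing here alters it.

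**2. Is admission CK a baseline value?** The draw is tied to admission (4.4) and allocation to the moment after catheter insertion (4.2.4, 4.3). The draw should normally come first. The documents do not state the order outright, so it needs confirming.

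**3. Gain from adjustment.** Assumptions that are not in the documents: correlation r between log admission CK and log later release; a true difference of 0.30 SD; 170 complete profiles per arm; two-sided 5%; normal approximation.

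- Residual variance = (1 − r²) × SD²
- SE = √(2/170) × √(1 − r²) = 0.1085 × √(1 − r²), in SD units
- Power = Φ(0.30/SE − 1.960)
- Difference detectable with 80% power = (1.960 + 0.8416) × SE

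| r | variance reduction | SE (SD units) | power at 0.30 SD | detectable difference (SD) |
|---|---|---|---|---|
| 0 (unadjusted) | 0% | 0.1085 | 79% | 0.304 |
| 0.2 | 4% | 0.1063 | 81% | 0.298 |
| 0.3 | 9% | 0.1035 | 83% | 0.290 |
| 0.5 | 25% | 0.0939 | 89% | 0.263 |
| 0.7 | 49% | 0.0775 | 97% | 0.217 |

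As an example, at r = 0.5: 0.30/0.0939 − 1.960 = 1.23, and Φ(1.23) = 0.89. Any further gain from the rhythm stratum is not counted, because nothing in the documents sizes it.

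**4. Chance imbalance.** An admission imbalance of two standard errors is 2 × 0.1085 = 0.217 SD. Unadjusted, it shifts the estimate by r × 0.217: 0.07, 0.11 and 0.15 SD at r = 0.3, 0.5 and 0.7.

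**5. Would change from admission do as well?** If admission and later values have equal SDs (assumed), the variance of a change score relative to the unadjusted value is 2(1 − r): 1.6, 1.4, 1.0 and 0.6 at r = 0.2, 0.3, 0.5 and 0.7. Regression gives 0.96, 0.91, 0.75 and 0.51. Below r = 0.5 a change score is noisier than ignoring the admission value altogether, so the choice of method matters.

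**The case against.** The plan is silent; it does not exclude the admission value. Release could mean a rise above admission, and section 7's general wording leaves room for regression. This stands: a reader might infer that the protocol discards the admission CK, but no section says so. The supportable statement is that its use is not specified.

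An unadjusted randomized comparison is valid, and chance imbalance is already reflected in its standard error. This also stands. Step 4 describes a loss of precision; it does not show bias.

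The size is assumed throughout. Neither r nor the 0.30 SD effect has a source in the documents, and at r of 0.2 or less the variance gain is 4% or less. Deaths during sampling would leave fewer than 170 complete profiles per arm and lower every power figure. This stands as a limit on size. It does not count against adjusting, since two covariates take the residual degrees of freedom only from 338 to 336.

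A stronger reading is that troponin, drawn at the same times, should replace total CK because CK also comes from skeletal muscle. The documents do not support it. They never call outcome 13 a measure of cardiac injury, and they say nothing on marker specificity or on a non-cardiac share. Repeat CPR and seizures after allocation belong to the intention-to-treat difference. Troponin need not be idle either: the adjudication committee receives laboratory results (10.2) and judges stent thrombosis, whose definition refers to myocardial infarction (6.5). Replacing a listed outcome would be a debatable protocol amendment.

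**Conclusion.** The point holds as one of specification and precision. Outcome 13 lacks a defined summary and a stated analysis, and a covariate that is already collected is not assigned to it. Adjustment would cut variance by between 4% (r = 0.2) and 49% (r = 0.7). For a 0.30 SD effect with 170 per arm, power would be between 81% and 97%, against 79% unadjusted. The gain is material only from about r = 0.5, and the documents do not allow r to be fixed. All of this assumes that the admission draw precedes allocation.

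Importance is low: one of 15 secondary outcomes is affected, the unadjusted test would be valid, and the primary analysis and N = 340 do not change. A reader might also infer that the mismatch between 24 h of sampling and a 48 h outcome is part of this point. It is a separate conflict between 4.4 and 5.2, and it concerns what can be measured, not how the arms are compared.

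**What to change.** In section 7, with a matching definition in 5.2 or section 6:

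1. Define CK release as one summary, either area under the curve or peak, over the post-admission samples, analysed on the log scale.
2. Compare the arms by linear regression adjusted for log admission CK and rhythm stratum (VT/VF versus asystole/PEA), reporting the treatment effect as a ratio with its 95% confidence interval.
3. Confirm in 4.4 that the admission sample is taken before the envelope is opened, and say what is done when it is not.
4. State how incomplete profiles, including deaths during sampling, are handled.
5. Reconcile the sampling period in 4.4 with the outcome window in 5.2 in the same edit, since the summary in item 1 depends on it.

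Troponin may be analysed in the same way as a supportive measure if the investigators wish; CK stays the listed outcome. Items 1 to 4 need wording only, with no added patients or blood draws. The cost of item 5 depends on how the two sections are reconciled.

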4.5 Discovery of Novel Biomarkers - Blood Samples

The purpose of the blood samples is to screen for potential biomarkers of prognosis in patients presenting with ROSC undergoing TH. To screen for identification of potential biomarkers 50 patients will be enrolled. Because of the need to process blood samples promptly, the first 50 patients presenting during regular working hours will be selected. Blood samples will be drawn at baseline, 12hrs, 24hrs, 48 hrs and 72hrs for a total of 5 samples. Each sample will be 5cc's and they will be drawn by the patient's nurse from the established cooling catheter thus requiring no additional venipuncture. Study co-investigators will be responsible for obtaining

blood samples from the nurses and processing the blood samples. In total, 25 cc's of blood will be drawn per patient. Therefore, a total of 1250 cc's of blood will be drawn in the context of this study.

Samples will be stored in the designated locked laboratory at the University of Ottawa Heart Institute for a period of one year at -80 degrees celsius. Samples will be de-identified by a number and linked to a password protected master list maintained on the University of Ottawa Heart Institute server and or secure network server.

Once samples from 50 patients have been collected we will screen for biomarkers of poor neurologic outcome (the primary outcome of the study) using unbiased screening technology. Specifically, we will screen serum levels of proteins using proteomics techniques which enable us to identify proteins with distinctly different levels between the groups. Secondly, we will screen for levels of circulating microRNA which may predict poor neurologic outcome. No genetic testing will be performed on the samples.

The goal of these studies is to identify previously unidentified markers of poor prognosis in ROSC patients which are needed to prognosticate outcomes at an early stage of their presentation.

4.6 Follow-up

Patients will be assessed by a cardiologist at the following time intervals – 1, 3, 6 months after the cardiac arrest. Patients will be seen by the rehabilitation specialist at 6 months after the cardiac arrest. Current standard of care for follow-ups for this population is for patients to be seen by a cardiologist at 1 and 6 months. However, if deemed to be necessary the cardiologist may decide to see a patient at a higher frequency. Follow-up with the rehabilitation specialist is likely to be done at 6 months but is determined on a case by case basis.

4.7 Pre-specified subgroups

The following pre-specified subgroups will be analyzed at the end of the study:

1. Ventricular tachycardia or ventricular fibrillation as initial rhythm
2. ST segment elevation myocardial infarction as index event
3. Patients taken to the cardiac catheterization laboratory within 12 hrs of the cardiac arrest event
4. Patients undergoing percutaneous coronary intervention
5. Patients age >75yrs

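### The PCI subgroup, and to a lesser degree the catheterization-laboratory subgroup, can be entered after randomization, so comparisons within them may not be between randomized groups

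*Combined protocol and SAP*

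**What the plan says.** Section 4.7 lists five subgroups for analysis at the end of the study. Three describe the patient or the index event: initial rhythm, "ST segment elevation myocardial infarction as index event", and age. The other two describe care received:

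- Subgroup 3: "Patients taken to the cardiac catheterization laboratory within 12 hrs of the cardiac arrest event".
- Subgroup 4: "Patients undergoing percutaneous coronary intervention".

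Subgroup 3 has a 12 h window, counted from the arrest. Subgroup 4 has no window.

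Section 4.2.4 fixes the time of allocation: "Patients will be randomized immediately following insertion of the endovascular cooling catheter". Section 4.3 says that this catheter is placed "either in the cardiac catheterization laboratory or in the coronary care unit".

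On catheterization, section 4.3 says: "Upon presentation to the University of Ottawa Heart Institute, patients may be taken to the cardiac catheterization laboratory at the discretion of the treating team". The purposes named there are "coronary angiography and/or insertion of a mechanical support device (intra-aortic balloon pump").

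Section 5.1 makes death a component of the primary outcome. Section 7 and its subsections give no method for the subgroups and no rule on when membership is determined.

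**The concern.** A within-arm subgroup keeps the protection of randomization only if membership is fixed before allocation or cannot be influenced by it. Subgroups 3 and 4 meet neither condition by definition. A patient who enters through a procedure done under the assigned temperature has been selected partly by what happened after allocation.

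This matters most for subgroup 4. A patient must live to a later PCI and be fit for it, while death counts as a primary outcome event. Membership can therefore depend in part on the endpoint being compared.

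At stake is how the result is read. The comparison would be reported as a pre-specified subgroup finding and taken as randomized evidence on whether the effect of 31°C differs in PCI patients. The complementary group (no PCI) would be affected too, and so would any contrast between the two.

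**Working it through.** **1. The plan's own figure.** No figure is given for any subgroup. The overall sample size reproduces. With 50% and 35%, two-sided alpha of 0.05, 80% power and pooled variance under the null:

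n per arm = [1.960·√(2·0.425·0.575) + 0.842·√(0.25 + 0.2275)]² / 0.15² = 169.3, rounded up to 170, or 340 in total.

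The point made here does not change this figure.

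**2. Who can enter after allocation.** Setting 4.2.4 and 4.3 beside 4.7:

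- *Randomized in the coronary care unit, no earlier laboratory visit.* Can enter subgroup 3 until 12 h after the arrest, and subgroup 4 at any later time.
- *Randomized in the laboratory, PCI not yet begun.* Already in subgroup 3 if arrival was within 12 h of the arrest. Can still enter subgroup 4.
- *PCI done or under way before the envelope is opened.* Membership of subgroup 4 is settled.

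Only the third case is free of the problem for subgroup 4. Nothing in the documents says how many patients fall in each.

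**3. Whether another section closes the gap.** Sections 7, 7.1 and 7.2 do not mention subgroups. Section 7.3 concerns description of the groups only. No section restricts membership to status before allocation.

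**4. How the arm could affect entry.** Section 4.3 foresees that a physician may judge that "cooling is contributing to intractable arrhythmia, or hypotension refractory to vasopressor use". Section 5.2 compares cardiogenic shock, repeat arrest, arrhythmia and death between arms. Section 7.1 hypothesizes fewer primary outcome events at 31°C. These routes point in different directions:

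- Instability or death may prevent a later PCI.
- Instability may bring a patient to the laboratory for mechanical support, which counts for subgroup 3.
- Better survival at 31°C may let more patients of poor prognosis reach a later PCI.

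The documents give no rate by arm for any of them.

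**5. Illustration, all inputs assumed.** Suppose temperature has no effect on outcome. In each arm a share *a* has PCI before allocation, with 50% events. A further share *l* has PCI after allocation, with event rate *r*; *r* is below 50% because these patients survived to PCI. The subgroup event rate in an arm is

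p = (0.5a + r·l)/(a + l),

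so, moderate minus mild,

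p₃₁ − p₃₄ = a(0.5 − r)(l₃₄ − l₃₁)/[(a + l₃₄)(a + l₃₁)].

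With a = 30%, r = 20%, l₃₄ = 10% and l₃₁ = 5%: p₃₄ = 0.17/0.40 = 42.5%, p₃₁ = 0.16/0.35 = 45.7%, a difference of +3.2 points. Reversing the arms gives −3.2. Equal late PCI (10% and 10%) gives 0.

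Over a = 20% to 40% and r = 10% to 30%:

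| Late PCI in the two arms | Spurious difference (either sign) |
|---|---|
| equal, equally selected | 0 |
| 10% and 5% | 1.8 to 5.3 points |
| 15% and 5% | 3.2 to 9.1 points |

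For scale, in the worked case the subgroup has 0.40 × 170 = 68 and 0.35 × 170 = 59.5 patients. The standard error of the difference is √(0.425·0.575/68 + 0.457·0.543/59.5) = 8.8 points.

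The illustration does not cover the routes through death, since these are themselves treatment effects on the outcome. It shows only that the sign follows whichever arm has more late PCI, and that the size can be nil.

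**The case against.** The strongest reply is that the problem is mostly theoretical. The decision to catheterize is placed at presentation (4.3), and the catheter that triggers randomization may be inserted in that same laboratory. The treating physician is blinded (4.2.5). The emergency orders in Appendix 9 say that PCI must not wait for cooling. Section 4.1 describes the centre's own work as primary PCI with hypothermia, and section 4.4 lists the post-PCI ECG among the early tests. Section 4.1 also calls stopping of cooling infrequent. All this suggests that PCI is meant mainly as an early, index procedure.

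Much of this stands. It weakens the point for subgroup 3, where a patient must be randomized first and still reach the laboratory within 12 h of the arrest. It also suggests that late PCI may be uncommon. It does not remove the point. The wording on catheterization is permissive, and no section sets a time limit for PCI. Blinding stops decisions made from knowledge of the arm; it does not stop temperature from changing who survives or is stable enough for PCI.

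A reader might go further and infer that these subgroup results will be biased, or biased in favour of 31°C. The documents do not support that. They give no share of PCI after allocation and no difference between arms, and the plausible routes run both ways. Nor do they show that STEMI as index event can replace the PCI subgroup: 4.7 lists the two separately, and Appendix 9 has its own path for patients who do not meet STEMI criteria.

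**Conclusion.** The point holds as one of definition. Subgroup 4 is open-ended relative to randomization. Subgroup 3 shares the weakness to a lesser degree, because its clock starts at the arrest and allocation can take place in the coronary care unit. Whether bias follows depends on an assumption that the documents neither make nor rule out: that the assigned temperature affects entry through survival or stability. If it does not, the bias is zero. Size and sign cannot be derived, and the 0 to 9 point range only shows what assumed inputs produce.

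The primary comparison, its sample size and its alpha are untouched. Severity is minor: a cheap improvement to secondary analyses.

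**What to change.** In 4.7, define the pre-specified form of both subgroups by status at the moment the randomization envelope is opened:

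- Subgroup 3: already taken to the catheterization laboratory, within 12 h of the arrest (yes/no).
- Subgroup 4: PCI already performed or started (yes/no).

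Derive both from recorded procedure and randomization times. Report any version that counts later catheterization or PCI only as an exploratory, post-randomization, non-causal description.

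The cost is a few sentences in 4.7 and two times to record or, for patients already enrolled, to retrieve where records allow. The case report form is not in the documents and may already capture them. The subgroups become somewhat smaller or different. In particular, a patient whose cooling catheter goes in just before PCI starts would count as no for subgroup 4. The claim that can be made about PCI after randomization becomes weaker. Patient care, sample size and the primary analysis do not change.
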